
PARTICIPANT AREA	DESCRIPTION
Sample Size	Up to 30 individuals initiating use of the study system in closed-loop mode, with the goal of at least 24 completing the trial
Treatment Groups	All participants will use the study-assigned Control-IQ pump in closed-loop mode.
Participant Duration	~8-12 weeks, depending on duration of run-in phase
Study Duration (planned)	~5 months from first enrollment until last participant visit
Protocol Overview/Synopsis	
After consent is signed, eligibility will be assessed. Eligible participants not currently using a Dexcom G6 CGM or using a Dexcom G6 CGM with <85% of possible glucose values captured during the 14 days prior to enrollment will initiate a CGM run-in phase of 2-4 weeks. Participants who skip or successfully complete the CGM run-in will be trained on use of the study pump in open-loop mode and will initiate a pump run-in phase of 2-4 weeks that will include insulin therapy adjustment to optimize open-loop glycemic control.
 
Participants who successfully complete the open-loop pump run-in will be trained on use of the study pump in closed-loop mode and will use the study system (pump and CGM) in closed-loop mode for 6 weeks.
 
Subjects will be asked to use programmed sleep activity each night and perform exercise challenges with exercise mode enabled at least once per week.
 
Questionnaires will be given at the screening visit after consent; before starting closed-loop use (Control-IQ Phase); and after 6 weeks of closed-loop use. Semi-structured interviews will be performed at the end of the study to better determine the experience of using the study device
 
Study Safety Plan:
 
Participants will be given a blood glucose and ketone meter to use throughout the study, and will be trained on their use by qualified staff. BGM readings will be performed in accordance with the study safety plan and per CGM manufacturer instructions. Ketone readings will be performed per the study safety plan.
 
Site investigators may adjust insulin delivery profile settings as needed throughout the study in accordance with their clinical practice.

\* Current use of Dexcom G6 CGM with at least 85% of possible readings captured during the 14 days prior to enrollment

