#### 4.1.2 System Use Guidelines

498 The participant will be instructed to use the system in closed-loop mode except if insulin is  
499 delivered by any means other than the study pump (e.g. injection of subcutaneous insulin via  
500 syringe in the event of infusion site failure). If insulin is delivered by any means other than the  
501 study pump, the participant will be instructed to turn off Control-IQ for approximately four hours.

502 The participant will also be instructed to contact study staff in case of illness with an elevated  
503 temperature >101.5 degrees Fahrenheit (38.6 degrees Celsius), other periods of significant illness,  
504 or during periods of use of medications such as epinephrine for the emergency treatment of a  
505 severe allergic reaction or asthma attack in addition to use of oral or injectable glucocorticoids to  
506 determine if closed-loop use should be temporarily discontinued.

507 Participants will be provided with sufficient supplies to last until the subsequent visit.

508 Participants will be provided with contact information and will be asked to call the study  
509 clinical staff for any health-related issues and for technical issues with the system. Participants  
510 may use the study pump without Control-IQ activated and study CGM during periods of  
511 component disconnections or technical difficulties.

512 Study staff will discuss with the participant that routine contact is required and will make  
513 arrangements for the contacts. If the participant cannot be reached, the participant's other contact  
514 methods will be utilized, including an emergency contact. Participants who are not compliant with  
515 the arranged contacts on two separate occasions may be discontinued at the discretion of the  
516 investigator.

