#### 5.2.3 Hypoglycemia Threshold Alarm and Safety Protocol

666 When using the study device, hypoglycemia low threshold alerts will be set to no lower than 70  
667 mg/dL, and if a participant's CGM reading is <70 mg/dL, subjects will be instructed to treat with  
668 ~15 grams of carbohydrate and perform fingerstick testing as necessary per CGM manufacturer  
669 instructions.

670                   **5.2.4 Hyperglycemia Threshold Alarm and Safety Protocol**

671   During the course of the study, participants will be permitted to change this setting, but will be  
672   instructed to choose a value no greater than 300 mg/dL.

673   During the CGM run-in and open-loop pump wear period, if a participant's CGM reading is  
674   >300 mg/dL for over 2 hours:

- 675   • Perform a blood glucose meter check.
- 676   • For bolus insulin users, if the blood glucose is >300 mg/dL, give a correction dose of insulin  
677    if no bolus has been given within the last hour. If blood glucose does not decrease by 50  
678    mg/dL within 90 minutes of the correction dose, contact study staff for further instructions.
- 679   • For basal insulin users, contact study staff for further instructions.

680   During the time period when the closed-loop system is operational and active, if a participant's  
681   CGM reading is >300 mg/dL for over 1 hour or ≥400 mg/dL at any point, or the participant  
682   experiences severe symptoms of hyperglycemia (nausea, vomiting, abdominal pain), the  
683   participant will be instructed to take the following steps:

- 684   • Perform a blood glucose meter check.
- 685   • If the blood glucose is >300 mg/dL, check for blood ketones with the study ketone meter.
- 686   • If the ketone level is ≥ 0.6 mmol/L (or ≥ 2.5 mmol/L at any time), take correction insulin,  
687    change insulin (pump) infusion site and contact study staff. Continue to monitor their  
688    glucose and blood ketone levels until they return to normoglycemia and ketones are < 0.6  
689    mmol/l.
  - 690    ◆ If ketones are <0.6 mmol/l, they will be advised to continue to monitor their glucose  
691    until it returns to normoglycemia and to repeat the ketone measurement in 90 minutes  
692    if necessary.
  - 693    ◆ If glucose fails to correct, or symptoms persist, contact study staff immediately for  
694    further instructions, to include giving a correction dose by injection.

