- 695   • If correction insulin is administered via insulin syringe, turn Control-IQ off for  
696    approximately four hours and until glucose level has returned to <180 mg/dL.
- 697   • If unable to contact study staff and the participant is vomiting, go to the Emergency  
698    Room.

699                   **5.3 Participant Access to Study Device at Study Closure**

700   Participants will be returned to their pre-study insulin therapy at the conclusion of the study and  
701   must return all study-assigned materials to the clinical site. Return of these materials must occur  
702   within 7 weeks (49 days) of initiation of closed-loop system use.

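### In the closed-loop hyperglycemia steps of Protocol 5.2.4, a participant with severe symptoms but a meter glucose of 300 mg/dL or below is not directed to test ketones

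*Protocol*

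**What the plan says.** Section 5.2.4 of the Protocol sets out what participants do about high glucose. For the closed-loop phase there are three alternative triggers. Two are CGM readings: above 300 mg/dL for over an hour, or 400 mg/dL or more at any point. The third needs no glucose value: when a participant "experiences severe symptoms of hyperglycemia (nausea, vomiting, abdominal pain), the" same steps begin.

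The first step, for every trigger, is a meter check. The second is "If the blood glucose is >300 mg/dL, check for blood ketones with the study ketone meter". The third acts on the result: "If the ketone level is ≥ 0.6 mmol/L (or ≥ 2.5 mmol/L at any time), take correction insulin", followed by an infusion-site change and a call to staff. Below 0.6 mmol/L, participants keep monitoring glucose and repeat the ketone test at 90 minutes if needed.

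Three safeguards do not depend on a ketone result or a glucose threshold, or need not be read as depending on one:

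- 5.2.4: "If glucose fails to correct, or symptoms persist, contact study staff immediately for" further instructions.
- 5.2.4: "If unable to contact study staff and the participant is vomiting, go to the Emergency" Room.
- 4.1.2: participants contact staff for fever and "other periods of significant illness", and are asked to call the study "clinical staff for any health-related issues and for technical issues with the system".

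Elsewhere, the Protocol Summary says only "Ketone readings will be performed per the study safety plan". Section 3.3 likewise points to the hyperglycemia safety plan, and 5.1.4 ties ketone measurement to prolonged hyperglycemia.

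**The concern.** Making symptoms a separate trigger accepts that they call for action whatever the CGM shows. The second step then puts a glucose condition back in front of the one test that bears on whether the symptoms are ketotic. The participant follows these steps alone at home, so the order in which they are written matters.

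The plan's own text gives reason to care. Section 1.4.1.3 says ketonemia could follow reduced or suspended insulin delivery or a pump or infusion-set fault, and that DKA, though less common than in type 1 diabetes, can still occur. In 7.2.4 the HHS criteria carry a typical glucose level (above 600 mg/dL). The DKA criteria apply to hyperglycemic events but set no numeric floor, so a reading of 300 mg/dL or below does not by itself rule DKA out under the protocol's definition. What is at stake is an early home ketone result in a participant who is already unwell.

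**Working it through.** No arithmetic applies. The check is to read the closed-loop steps as a decision tree and then look for any other instruction that fills an empty branch.

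**Inputs.** Triggers, meter step, ketone-test condition and later actions: Protocol 5.2.4. Other mentions of ketone testing: Protocol Summary, 3.3 and 5.1.4. General contact rules: 4.1.2.

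**Step 1: the tree.**

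| Branch | Trigger | Meter glucose | Ketone self-test directed? |
|---|---|---|---|
| a | CGM reading | above 300 | Yes |
| b | CGM reading | 300 or below | No |
| c | Severe symptoms | above 300 | Yes |
| d | Severe symptoms | 300 or below | No |

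Branch b is reasonable: the trigger was a sensor glucose value, and the meter has failed to confirm it. Branch d is different: the trigger was symptoms, and a meter glucose does not settle their cause.

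**Step 2: do the later steps of 5.2.4 fill branch d?** The 0.6 mmol/L line, the 2.5 mmol/L clause and the 90-minute repeat all act on, or follow, a ketone value already obtained. The words attached to 2.5 mmol/L set a level for action; they do not order a test. They also add no separate action, since any value of 2.5 or more already meets 0.6 and the written response is the same. What was meant by them is unclear.

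**Step 3: do other sections fill it?** The Summary and 3.3 refer back to the safety plan. Section 5.1.4 speaks of prolonged hyperglycemia, which branch d does not establish. Section 4.1.2 directs a call, not a test. None of them directs a ketone self-test for symptoms at 300 mg/dL or below.

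**Step 4: what does branch d still have?** The 4.1.2 calls apply without a glucose condition. The persisting-symptoms line in 5.2.4 sits beneath the ketone-result bullet, so whether it reaches someone who never tested is a matter of reading. The Emergency Room line needs both vomiting and failure to reach staff. Staff may ask for a ketone test once called, but the Protocol does not say so.

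**Step 5: what happens if a test is added?** The ketone-action bullet has no explicit glucose condition of its own. A new test at 300 or below would lead into that bullet, including its correction insulin, unless the text says what is intended there. The fix has to address this.

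**The case against.** The strongest defence is that this is a coherent design: ketone testing is tied to glucose, and illness is routed to study staff. Section 3.6.3 describes the closed-loop guidelines by glucose level, and 5.1.4 is consistent with that. Participants also receive written guidance (1.4.1.3, 3.3, 3.6.3) that is not in the documents and could already cover this case. Both points limit the weight of the finding. Neither removes the mismatch inside 5.2.4, where symptoms open the steps but cannot by themselves open the ketone test.

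Four stronger readings are tempting and are not supported:

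- **Symptomatic participants have no safeguard.** They have the three listed above, and the 4.1.2 calls carry no glucose condition.
- **The SAP's ketone-event rate is materially biased.** SAP section 8 counts days with ketones above 1.0 mmol/L, and an untested day cannot be counted. But testing is event-triggered throughout, so that count is incomplete in any case, and nothing in the documents says how often branch d would occur. Dividing one event by total exposure gives the weight of any missed event from any cause; it does not measure this gap.
- **Permitted SGLT-2 inhibitors make the gap serious.** Section 8.3 allows stable doses and says nothing about ketosis at lower glucose. That link would be outside clinical judgement and carries no weight here.
- **The treatment steps should be rewritten too.** Restricting correction insulin to glucose above 300, or adding an Emergency Room rule at 2.5 mmol/L, would change treatment on no basis in the documents. The first might withdraw insulin that the present wording directs.

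**Conclusion.** The point holds in a narrow form. Of the four branches in the closed-loop steps, the one for severe symptoms with a meter reading of 300 mg/dL or below has no directed ketone self-test, and no other section supplies one. The gap is early self-testing only.

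Confidence is high for what 5.2.4 says. It is lower for what participants are actually told, because the handout and procedures manual are not available. No frequency, event rate, efficacy result or stopping rule is affected or claimed. The change is worth making because it is cheap and follows from the protocol's own choice to treat symptoms as a trigger.

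**What to change.** In the second closed-loop step of 5.2.4, widen the condition so that the ketone check is done if meter glucose is above 300 mg/dL, or if severe symptoms are present at any glucose level.

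Add one line: if ketones are 0.6 mmol/L or more and glucose is 300 mg/dL or below, the participant contacts study staff immediately. Leave insulin and carbohydrate dosing at that glucose level to the sponsor's clinicians, and ask them to state what the 2.5 mmol/L clause is meant to do. Make the participant handout match; if it already contains the instruction, bring 5.2.4 into line with it.

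The cost is a few lines of text and, per episode, one or two strips (the first test plus the existing optional repeat at 90 minutes). There would be some extra staff calls. Ketosis for which the site gives guidance is reportable under 7.2.4, so a few more adverse events may be recorded.

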## Chapter 6: Testing Procedures and Questionnaires

## 6.1 Laboratory Testing

## 1. HbA1c:

- HbA1c level measured using the DCA2000 or comparable point of care device or local lab at the Screening visit, if no comparable measurement is available from the 2 weeks prior to enrollment
- HbA1c level measured at a Central Lab from blood draw performed at Screening visit

C-peptide/Glucose:

- C-peptide with concurrent glucose level measured at a Central Lab from blood draw performed at Screening visit

Urine Pregnancy:

- Performed locally for females of child-bearing potential at Screening and at the Control IQ phase initiation visit. This will also be done anytime pregnancy is suspected.

*Local laboratory testing will be performed if needed to screen for exclusionary medical conditions.*

## 6.2 Electrocardiogram (ECG)

719 An ECG will be administered using the clinic's ECG machine and read locally by the  
720 investigator at the Screening visit to determine if the participant meets eligibility criteria with  
721 respect to the exercise component of the study. The printed ECG with the investigator's  
722 evaluation, signature and date must be saved in the study records (note – making a copy of the  
723 ECG once signed preserves the integrity of the read due to the fragility of the printer paper).

### 6.3 Questionnaires

725 Questionnaires are completed by all participants at the study visits indicated in the table below.

726 Each questionnaire is described briefly below. The procedures for administration are described  
727 in the study procedures manual.

**728 Table 3.** Study Questionnaire Summary

MEASURE	CONSTRUCT MEASURED/RELEVANT POINTS	ADMINISTRATION POINTS
Tandem Study-Specific Baseline Survey	A Tandem-specific 4-item questionnaire that captures information about Healthcare Provider relationships, comfort with new technologies for diabetes management, and comfort understanding written information. (3 mins)	
 
Screening Visit
 

Altarum Consumer Engagement (ACE) Measure – Commitment Subscale	A 6-item questionnaire measuring commitment to everyday health behaviors. Predicts overall health, adherence to medical guidance, and success at chronic disease management. (2 mins)	
 
Screening Visit
 

MEASURE	CONSTRUCT MEASURED/RELEVANT POINTS	ADMINISTRATION POINTS
Tandem Pump Training Survey	A Tandem-specific 4-item questionnaire that captures patient-reported experience with Tandem pump training, including overall satisfaction and time investment. (3 mins)	
 
• Pump Run-In Initiation Visit
 
• Control-IQ Initiation Visit
 

DAWN Impact of Diabetes Profile (DIDP)	A 7-item questionnaire providing a valid and reliable measure of the perceived impact of diabetes on quality of life, suitable for adults with Type 1 or Type 2 diabetes mellitus. (2 mins)	
 
• Screening Visit
 
• Control-IQ Initiation Visit
 
• 6-Week Visit
 

Diabetes Impact and Device Satisfaction (DIDS) Scale	A 12-item questionnaire focused on satisfaction related to insulin delivery devices (e.g., trust and ease of use) and diabetes-related impact on daily life, such as worry around hypoglycemia and sleep interruptions. (3 mins)	
 
• Screening Visit
 
• Control-IQ Initiation Visit
 
• 6-Week Visit
 

PROMIS Sleep-Related Impairment Questionnaire	An 8-item questionnaire that measures sleep disturbance and sleep-related impairment. (2 mins)	
 
• Screening Visit
 
• Control-IQ Initiation Visit
 
• 6-Week Visit
 

System Usability Scale (SUS)	A 10-item questionnaire that measures the overall usability of a system. It is a valid and reliable measure of the perceived usability of a system and is technology-agnostic. (2 mins)	
 
• Control-IQ Initiation Visit
 
• 6-Week Visit
 

729

730

#### 6.4 Semi-Structured Interviews

731 A semi-structured one-on-one interview may be completed concurrent with the 6-Week Visit or  
 732 within a 28-day period following that visit. The interview will last approximately 30 minutes and  
 733 will be conducted by Tandem staff using a script of open-ended questions to gather feedback and  
 734 reactions to the closed loop system, the clinical trial, and QoL changes.

735 Interview sessions may be audio- or video-taped and transcribed by a professional transcription  
 736 service. Otherwise, these recordings will not be shared for any non-study purposes.  
 737 Transcriptions will use a code for participants, such as “Participant 1”, and will not contain  
 738 names or other identifiers of participants.

739 **Chapter 7: Unanticipated Problem, Adverse Event, and Device Issue**  
740 **Reporting**

741 **7.1 Unanticipated Problems**

742 Site investigators will promptly report all unanticipated problems meeting the criteria below on  
743 an eCRF. Sites overseen by the JCHR IRB must report Unanticipated Problems to the IRB  
744 within seven (7) calendar days of recognition. For this protocol, an unanticipated problem is an  
745 incident, experience, or outcome that meets all of the following criteria:

- 746 • Unexpected (in terms of nature, severity, or frequency) given (a) the research procedures  
747 that are described in the protocol related documents, such as the IRB-approved research  
748 protocol and informed consent document; and (b) the characteristics of the subject  
749 population being studied
- 750 • Related or possibly related to participation in the research (possibly related means there  
751 is a reasonable possibility that the incident, experience, or outcome may have been  
752 caused by the procedures involved in the research)
- 753 • Suggests that the research places participants or others at a greater risk of harm than was  
754 previously known or recognized (including physical, psychological, economic, or social  
755 harm)

756 An example of an unanticipated problem in this study would be incidence rates of hypo- or  
757 hyperglycemia in the study (T2D) population, related to closed-loop insulin delivery, that are  
758 significantly higher than previously encountered when using the study system in the T1D  
759 population.

760 The Coordinating Center also will report to the IRB all unanticipated problems not directly  
761 involving a specific site such as unanticipated problems that occur study-wide or at another  
762 participating entity such as a pharmacy or laboratory. These instances must be reported to the  
763 JCHR IRB within seven (7) calendar days of recognition. The Director of the Human Research  
764 Protection Program (HRPP) will report to the appropriate regulatory authorities if the IRB  
765 determines that the event indeed meets the criteria of an Unanticipated Problem requiring  
766 additional reporting to fulfill the reporting obligations of the HRPP.

767 **7.2 Adverse Events**

768 **7.2.1 Definitions**

769 Adverse Event (AE): Any untoward medical occurrence (including laboratory findings)  
770 associated with study procedures, the use of a device, biologic, or drug in humans, including any  
771 comparator used, whether or not the event is considered related (i.e., irrespective of the  
772 relationship between the adverse event and the device(s) under investigation).

773 Serious Adverse Event (SAE): Any untoward medical occurrence that results in any of the  
774 following outcomes:

775 • Death.

776 • A life-threatening adverse event; (a non-life-threatening event which, had it been more  
777 severe, might have become life-threatening, is not necessarily considered a serious adverse  
778 event).  
779 • Inpatient hospitalization or prolongation of existing hospitalization.  
780 • A persistent or significant disability/incapacity or substantial disruption of the ability to  
781 conduct normal life functions (sight threatening).  
782 • A congenital anomaly or birth defect.

783 An important medical event that may not result in death, be life-threatening, or require  
784 hospitalization may be considered serious when, based upon appropriate medical judgment, it  
785 may jeopardize the patient or subject and may require medical and surgical intervention to  
786 prevent one of the outcomes listed in this definition. Note: If either the Sponsor or investigator  
787 believes that the event is serious, the event must be considered serious and evaluated by the  
788 Sponsor for expedited reporting.

789 Unanticipated Adverse Device Effect (UADE): Any serious adverse effect on health or safety or  
790 any life-threatening problem or death caused by, or associated with, a device, if that effect,  
791 problem, or death was not previously identified in nature, severity, or degree of incidence in the  
792 investigational plan or application (including a supplementary plan or application), or any other  
793 unanticipated serious problem associated with a device that relates to the rights, safety, or  
794 welfare of participants (21 CFR 812.3(s)).

795 Adverse Device Effect (ADE): An adverse event related to the use of an investigational medical  
796 device. This definition includes adverse events resulting from insufficient or inadequate  
797 instructions for use, deployment, implantation, installation, or operation, or any malfunction of  
798 the investigational medical device. This definition includes any event resulting from use error or  
799 from intentional misuse of the investigational medical device. This includes comparator if the  
800 comparator is a medical device. (Note that an Adverse Event Form is to be completed in addition  
801 to a Device Deficiency or Issue Form, unless excluded from reporting as defined in section 8.2).

802 Comparator: Medical device, therapy (e.g. active treatment, normal clinical practice), placebo or  
803 no treatment, used in the control group in a clinical investigation. (ISO 14155:2020)

804 Device Complaints and Malfunctions: A device complication or complaint is something that  
805 happens to a device or related to device performance, whereas an adverse event happens to a  
806 participant. A device complaint may occur independently from an AE, or along with an AE. An  
807 AE may occur without a device complaint or there may be an AE related to a device complaint.  
808 A device malfunction is any failure of a device to meet its performance specifications or  
809 otherwise perform as intended. Performance specifications include all claims made in the  
810 labeling for the device. The intended performance of a device refers to the intended use for  
811 which the device is labeled or marketed. (21 CFR 803.3). Note: for reporting purposes, sites will  
812 not be asked to distinguish between device complaints and malfunctions.

813 Use Error: User action or lack of user action while using the medical device (3.34) that leads to a  
814 different result than that intended by the manufacturer or expected by the user. Includes the  
815 inability of the user to complete a task. Use errors can result from a mismatch between the  
816 characteristics of the user, user interface, task or use environment. Users might be aware or  
817 unaware that a use error has occurred. An unexpected physiological response of the patient is not

818 by itself considered a use error. A malfunction of a medical device that causes an unexpected  
819 result is not considered a use error. (ISO 14155:2020)

820

821 **7.2.2 Reportable Adverse Events**

822 For this protocol, a reportable adverse event includes any untoward medical occurrence that  
823 meets one of the following criteria:

- 824 1. An SAE as defined in section 7.2.1
- 825 2. An ADE as defined in section 7.2.1, unless excluded from reporting in section 7.3
- 826 3. An AE as defined in 7.2.1 occurring in association with a study procedure
- 827 4. An AE as defined in 7.2.1 not related to a device issue which leads to temporary or  
828 permanent discontinuation of a study device
- 829 5. An AE as defined in 7.2.1 that affects the participant's ability to complete any study  
830 procedures
- 831 6. An AE as defined in 7.2.1 for which a visit is made to a hospital emergency department
- 832 7. Hypoglycemia meeting the definition of reportable hypoglycemia as defined below
- 833 8. Diabetic ketoacidosis (DKA) or hyperosmolar hyperglycemic syndrome (HHS) as defined  
834 below; or in the absence of DKA/HHS, hyperglycemia or ketosis event meeting the criteria  
835 defined below.

836 Hypoglycemia and hyperglycemia not meeting the criteria below will not be recorded as adverse  
837 events unless associated with an Adverse Device Effect or discontinuation of the study device.  
838 Skin reactions from sensor placement are only reportable if severe and/or required treatment.

839 All reportable AEs—whether volunteered by the participant, discovered by study personnel  
840 during questioning, or detected through physical examination, laboratory test, or other means—  
841 will be reported on an AE form online. Each AE form is reviewed by the Medical Monitor to  
842 assess safety and to verify the coding and the reporting that is required.

843 **7.2.3 Hypoglycemic Events**

844 Hypoglycemia not associated with an Adverse Device Effect or discontinuation of the study  
845 device is only reportable as an adverse event when one of the following criteria is met:

- 846 • a hypoglycemic event occurred meeting the following definition of severe hypoglycemia:  
847 the event required assistance of another person due to altered consciousness, and required  
848 another person to actively administer carbohydrate, glucagon, or other resuscitative  
849 actions. This means that the participant was impaired cognitively to the point that he/she  
850 was unable to treat himself/herself, was unable to verbalize his/ her needs, was  
851 incoherent, disoriented, and/or combative, or experienced seizure or loss of  
852 consciousness. These episodes may be associated with sufficient neuroglycopenia to  
853 induce seizure or loss of consciousness. If glucose measurements are not available  
854 during such an event, neurological recovery attributable to the restoration of glucose to

855                   normal is considered sufficient evidence that the event was induced by a low glucose  
856                   concentration.

857                   • evaluation or treatment was obtained at a health care provider facility for an acute event  
858                   involving hypoglycemia, or the participant contacted the site and received guidance  
859                   following the occurrence of an acute event involving hypoglycemia

860                   When a severe hypoglycemia event occurs (as defined above), a Hypoglycemia Form should be  
861                   completed in addition to the Adverse Event Form. Severe hypoglycemia events should be  
862                   considered to be serious adverse events with respect to reporting requirements. When a severe  
863                   hypoglycemia event occurs during use of a study device, it generally will be considered to be  
864                   unrelated to the device (per section 7.2.5) if the device functioned as intended and there does not  
865                   appear to be a flaw in how the device is intended to function.

866                   **7.2.4 Hyperglycemic/Ketotic Events**

867                   Hyperglycemia not associated with an Adverse Device Effect or discontinuation of the study  
868                   device is only reportable as an adverse event when one of the following criteria is met:

869                   • the event involved DKA, as defined by the Diabetes Control and Complications Trial  
870                   (DCCT) and described below

871                   • the event involved hyperosmolar hyperglycemic syndrome (HHS), as defined by the  
872                   American Diabetes Association and described below

873                   • evaluation or treatment was obtained at a health care provider facility for an acute event  
874                   involving hyperglycemia or ketosis, or the participant contacted the site and received  
875                   guidance on how to manage the hyperglycemia/ketosis

876                   Hyperglycemic events are classified as DKA if the following are present:

877                   • Symptoms such as polyuria, polydipsia, nausea, or vomiting;

878                   • Serum ketones  $>1.5$  mmol/L or large/moderate urine ketones;

879                   • Either arterial blood pH  $<7.30$  or venous pH  $<7.24$  or serum bicarbonate (or CO2)  $<15$ ; and

880                   • Treatment provided in a health care facility

881                   Hyperglycemic events are classified as HHS if the following are present:

882                   • Symptoms such as polyuria, polydipsia, nausea, or vomiting;

883                   • Plasma glucose levels are very elevated (typically  $>600$  mg/dL);

884                   • Plasma effective osmolarity is  $>320$  mOsm/L;

885                   • Absence of significant ketones; and

886                   • Treatment provided in a health care facility

887                   When a hyperglycemia/ketotic event qualifies as an SAE as defined in section 7.2.1 , a  
888                   Hyperglycemia/DKA Form should be completed in addition to the Adverse Event Form. Events  
889                   meeting DKA or HHS criteria should be considered to be serious adverse events with respect to  
890                   reporting requirements. Hyperglycemia events not meeting criteria for DKA or HHS generally

891 will not be considered as serious adverse events unless one of the SAE criteria in section 7.2.1 is  
892 met.

893 When a hyperglycemia/DKA event occurs during use of a study device, it generally will be  
894 considered to be unrelated to the device (per section 7.2.5) if the device functioned as intended  
895 and there does not appear to be a flaw in how the device is intended to function.

